1 PROTOCOL SUMMARY

1.1 SYNOPSIS

Title: A Phase Ib Trial of Inhaled Carbon Monoxide for the Treatment of Pneumonia and Sepsis-induced Acute Respiratory Distress Syndrome (ARDS)

Study Description: Multi-center, prospective, randomized, partially double-blind, placebo-controlled Phase Ib safety clinical trial of inhaled CO (iCO) for the treatment of pneumonia and sepsis-induced ARDS.

Hypothesis: We hypothesize that low dose iCO will be safe and well-tolerated and that the Coburn-Forster-Kane (CFK) equation-based iCO personalized dosing algorithm will be accurate in achieving a target carboxyhemoglobin (COHb) level of 6-8% in intubated patients with pneumonia and sepsis-induced ARDS.

Objectives: **Primary Objective:** To evaluate the safety and accuracy of a CFK equation-based personalized iCO dosing algorithm in intubated patients with pneumonia and sepsis-induced ARDS.

Secondary Objectives: To examine the effects of low dose iCO therapy on biologic readouts in intubated patients with pneumonia and sepsis-induced ARDS.

Endpoints: **Primary Endpoints:** The primary endpoints are:

1. **Safety of iCO**, defined by the incidence of pre-specified administration-related adverse events (AEs) and serious adverse events (SAEs). Administration-related SAEs are: 1) myocardial infarction; 2) stroke; 3) new onset arrhythmia requiring DC cardioversion; 4) worsening hypoxemia^{1,2}; 5) COHb $\geq 10\%$; and 6) increase in lactate by ≥ 2 mmol/L.

2. **Accuracy** of the CFK equation-based personalized iCO dosing algorithm to achieve a COHb level of 6-8%.

Secondary Endpoints:

1. Lung Injury Score (LIS) on days 1-5 and day 7
2. PaO₂/FiO₂ on days 1-5 and day 7
3. Oxygenation index (OI) on days 1-5 and day 7
4. Dead space fraction (Vd/Vt) on days 1-3 and day 7
5. Sequential Organ Failure Assessment (SOFA) scores on days 1-5, 7, 14, and 28
6. Ventilator-free days at day 28
7. ICU-free days at day 28
8. Hospital-free days to day 60
9. Hospital mortality to days 28 and 60
10. Neurocognitive function at 3 and 6 months

[figure not shown]
Exploratory Endpoints:

1. Blood and urine biomarkers of mitochondrial dysfunction (mtDNA), inflammasome activation (IL-18) and necroptosis (RIPK3)

2. Lipid mediators (LM) and specialized pro-resolving mediators (SPMs)

| | |
|--|---|

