| Renal replacement therapy status | X | X | X | X | X | X | X | X | X | | | | |
| Concomitant medications | X | X | X | X | X | X | X | | | | | | |
| Adverse event monitoring ^H | | X | X | X | X | X | X | X ^H | | | | | |

| Measurement/Event | Baseline | Day 1 | Day 2 | Day 3 | Day 4 | Day 5 | Day 7 | Day 14 | Day 28 | Day 60 | 3M | 6M | Post-discharge Call ^K |
|--|----------|-------|-------|-------|-------|-------|-------|--------|--------|--------|----|----|----------------------------------|
| Plasma isolation | | X | X | X | | | X | | | | | | |
| RNA banking | | X | X | X | | | X | | | | | | |
| DNA banking – Cell pellet isolation | | X | X | X | | | X | | | | | | |
| Primary cell (PBMC) isolation | | X | | | | | X | | | | | | |
| Urine sample collection | | X | X | X | | | X | | | | | | |
| Discarded BAL and plasma ^I | A | A | A | A | A | A | A | | | | | | |
| Microbiological results ^J | A | A | A | A | A | A | A | A | | | | | |
| Vital Status | | | | | | | | | | X | X | X | X |
| Discharge Status | | | | | | | | | | X | X | | X |
| Ventilator Status | | | | | | | | | | X | X | | X |
| Vasopressor Status | | | | | | | | | | X | X | | X |
| Neurocognitive Outcomes-MoCA-BLIND, Hayling | | | | | | | | | | | X | X | |

X - Required

A - When available

B - Data gathered at times indicated or until patient achieves 48 hours of unassisted breathing, whichever is sooner. Data will be obtained pre and post-treatment on study drug administration days.

C - Measure during reference period (03:00-10:00), obtain at time closest to study drug administration if applicable

D - CXRs done for clinical purposes will be reviewed on days 1-5. If the subject is extubated during days 1-5, a chest X-ray will be ordered by the study team the day following extubation, if not ordered by the clinical team.

E - Record clinically available creatinine, platelets, bilirubin, SBP and vasopressor use

F - Gathered on day 28 or on discharge date

G - Daily on days of study drug administration

H - AEs will be captured until study day 7

I - Obtained from discarded biobank (site specific) if available

J - Microbiological results recorded as they become available

K - If the subject is discharged home or to a long-term acute care facility before Day 28 or 60, he or she will be contacted by phone.

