6.1.6 DAILY HOLD PARAMETERS PRIOR TO STUDY DRUG ADMINISTRATION

Subjects will be assessed daily prior to study drug administration as described in the **Schedule of Activities (Section 1.3)**.

Administration of the study drug will be held if the following criteria are met.

- COHb level $\geq 3\%$
- Lactate ≥ 4 mmol/L
- ST elevation MI or unstable angina/non ST elevation MI concerning for ACS
- Unstable atrial or ventricular arrhythmia

Subjects will have blood drawn daily for measurement of COHb and lactate prior to administration of study drug. If COHb $\geq 3\%$ or lactate ≥ 4 mmol/L, the study drug will be held until the next scheduled dose the following day. Lactate and COHb will be measured the following day to determine whether the study drug will be administered. If the study drug is being held for another reason, COHb levels will not be measured on days the study drug is being held.

A 12 lead EKG will also be performed and reviewed daily by the study staff physician prior to study drug administration to evaluate for cardiac exclusion criteria (eg. acute MI, acute coronary syndrome (ACS), or unstable atrial or ventricular arrhythmia). If a subject meets the following criteria for ST elevation MI or unstable angina/non ST elevation MI concerning for ACS according to the American College of Cardiology Foundation/American Heart Association guidelines¹⁴⁰⁻¹⁴², they will be excluded from enrollment or further study drug administration according to exclusion criteria.

ST elevation MI (STEMI) Criteria: New ST elevation at the J point in at least 2 contiguous leads of ≥ 2 mm (0.2 mV) in men or ≥ 1.5 mm (0.15 mV) in women in leads V2–V3 and/or of ≥ 1 mm (0.1 mV) in other contiguous chest leads or the limb leads; New or presumably new left bundle branch block (LBBB)¹⁴⁰⁻¹⁴².

Unstable angina/non ST elevation MI (NSTEMI): Ischemic ST-segment depression ≥ 0.5 mm (0.05 mV) or dynamic T-wave inversion with pain or discomfort; Nonpersistent or transient ST-segment elevation ≥ 0.5 mm for < 20 minutes. Threshold values for ST-segment depression consistent with ischemia are J-point depression 0.05 mV (-0.5 mm) in leads V2 and V3 and -0.1 mV (-1 mm) in all other leads (men and women)¹⁴⁰⁻¹⁴².

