6.1.8 PERMANENT DISCONTINUATION OF STUDY DRUG

Permanent discontinuation of the study drug is defined as cessation of the study drug without the intent of restarting the study drug during the three-day treatment period.

Permanent discontinuation of the study drug inhalation will occur in the following situations:

- **Occurrence of pre-specified administration-related AEs:**
 - Acute MI* within 48 hours of study drug administration
 - Acute stroke** within 48 hours of study drug administration
 - New onset atrial or ventricular arrhythmia requiring DC cardioversion within 48 hours of study drug administration
 - Increased oxygenation requirements defined as: an increase in FiO₂ of ≥ 0.2 AND increase in PEEP ≥ 5 cm H₂O within 6 hours of study drug administration.
 - Increase in any protocol-specified measurement of COHb ≥ 10%
 - Increase in lactate by ≥ 2 mmol/L within 6 hours of study drug administration
- If the subject experiences serious adverse events (SAEs) **related to the study drug**
- If the investigator, attending physician, the patient or their surrogate decides that the study drug should be discontinued. If this decision is made because of an AE, then appropriate AE reporting procedures will be followed (**Section 8.7**).
- Daily baseline COHb levels ≥ 3% leading to three missed drug doses
- Three or more missed drug doses due to AEs

* Acute MI is defined below according to the Executive Group on behalf of the Joint European Society of Cardiology (ESC)/American College of Cardiology (ACC)/American Heart Association (AHA)/World Heart Federation (WHF) Task Force for the Universal Definition of Myocardial Infarction¹⁴⁴. We will also rely upon subspecialty consultation to confirm the presence or absence of an acute MI.

Acute myocardial infarction is defined as acute myocardial injury with clinical evidence of acute myocardial ischemia and with detection of a rise and/or fall of cardiac troponin values with at least 1 value above the 99th percentile upper reference limit and at least 1 of the following:

- Symptoms of myocardial ischemia;
- New ischemic ECG changes;
- Development of pathological Q waves;
- Imaging evidence of new loss of viable myocardium or new regional wall motion abnormality in a pattern consistent with an ischemic etiology;
- Identification of a coronary thrombus by angiography or autopsy (not for types 2 or 3 MIs).

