- 23. Concomitant Medications Review
- 24. Discarded bronchoalveolar lavage (BAL) fluid and plasma if available

8.5 STUDY DRUG ADMINISTRATION DAYS 1 – 3

Study Day 1 will be within 24 hours of randomization. Prior to treatment on each study day, blood will be drawn for measurement of COHb level, complete blood count (CBC), lactate, blood gas analysis (either ABG or venous blood gas [VBG]), and additional laboratory values (as outlined in **Section 1.3**) if not ordered by the clinical team as part of routine ICU care. The subject's chart will be reviewed daily for

interval medical events. The subject's ventilator settings, vital signs, laboratory values, EKG, chest X-ray, and concomitant medications will be reviewed to determine if the subject remains eligible for treatment on each study day. Daily Hold Parameters are outlined in **Section 6.1.6**.

If the subject remains eligible for treatment, the study visit will require approximately 3 hours. Treatment will last 90 minutes with additional safety monitoring for an additional 90 minutes immediately following study drug completion. Blood will be drawn at serial time point during treatment and after treatment for measurement of COHb levels and blood gas analysis (**Table 5**).

- Blood collection for COHb measurements pre-treatment and after 20 minutes for estimation of DLCO and determination of CFK-equation determined iCO dose to achieve a COHb level of 7% (target 6-8%) at 90 minutes (in subjects randomized to CO)
- Blood collection for COHb measurements at 40 minutes, 60 minutes, 75 minutes, 90 minutes, and 3 hours for safety monitoring
- Arterial or venous blood collection for blood gas analysis pre-treatment and at 90 minutes
- Blood collection for research labs (EDTA and PAXgene tubes) pre- and post-treatment (90 min, 3 hours)
- Urine collection for research labs pre- and post-treatment (90 min, 3 hours)

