8.5.2 PRE-TREATMENT ASSESSMENTS (DAY 1 – 3)

The following assessments will be done on Days 1-3 prior to study drug administration. **No treatment will be started before these assessments are performed and the pre-treatment administration checklist is completed by the study investigator.**

- **Blood Gas Analysis (arterial or venous):** Arterial or venous blood will be drawn for blood gas analysis using the IL GEM Premier Co-oximeter or local laboratory at each center. The blood gas will be assessed daily prior to starting study drug administration. The study drug will not be started until this result is obtained and reviewed by the study physician investigator for a potential study hold. The following values will be recorded from the ABG or VBG results: pH, PCO₂, PO₂, and base excess or deficit.
- **Hemoglobin Level:** Hemoglobin will be measured and assessed daily prior to study drug administration. The hemoglobin level will be measured by the local laboratory at each center. The study drug will not be started until this result is obtained and reviewed by the study physician investigator for a potential study hold.
- **COHb Level:** The baseline COHb level will be drawn and assessed by an unblinded physician investigator, just prior (less than 15 minutes) to starting the study drug administration. COHb will be measured by study investigators using an IL GEM Premier Co-oximeter at the subject's bedside. These results are obtained within less than 5 minutes. The study drug will not be started until this result is obtained and reviewed for a potential study hold. All COHb level result printouts should be filed in the unblinded subject file.
- **Lactate Level:** Lactate level will be measured and assessed daily by the local laboratory at each center prior to study drug administration. The study drug will not be started until this result is obtained and reviewed by the study physician investigator for a potential study hold.
- **EKG:** A 12 lead EKG will be obtained and reviewed daily by the study staff physician prior to study drug administration to evaluate for cardiac exclusion criteria (acute MI, ACS, or unstable atrial or ventricular arrhythmia). The study drug will not be started until the EKG is obtained and reviewed by the study physician investigator for a potential study hold. The EKG will also be officially read locally at each site.

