8.5.3 STUDY DRUG ADMINISTRATION AND MONITORING

The study drug will be administered for up to 90 minutes daily for up to 3 days following randomization or until discontinuation of mechanical ventilation, whichever occurs first according to **Section 6.1.9**. See **Sections 6.1.6, 6.1.7, and 6.1.8** for information about study drug hold, interruption, and permanent discontinuation criteria.

Study Drug Dosing:

Subjects randomized to CO will be administered iCO at 200 ppm for 20 min as a “test dose” on each treatment day to determine in real-time each subject’s CFK equation-determined personalized dose. COHb levels will be measured before and after the 20 min test dose, and these two levels entered into the CFK equation calculator program to estimate DL_{CO} and compute the iCO dose to achieve a COHb level of 7% (target 6-8%) at 90 min. After the iCO dose is determined, subjects will be administered iCO at the CFK equation-determined personalized dose (200-500 ppm) but not to exceed 500 ppm or 90 min total (including test dose). Subjects randomized to placebo will be administered air.

Monitoring during Study Drug Administration:

Subjects will be monitored with continuous pulse oximetry, cardiac monitoring, and either intermittent (at least every 15 minutes) or continuous blood pressure monitoring (if an arterial line is in place) throughout the course of the 90-minute study drug treatment.

$SpCO$ and SpO_2 will be monitored continuously using a Masimo Rad-7 non-invasive pulse oximeter, and recorded at the time points specified in **Table 5**. COHb levels will be measured using an IL GEM Premier Co-oximeter and recorded at the time points specified below. Arterial or venous blood will be drawn for blood gas analysis prior to treatment and at the completion of study drug administration (90 min or earlier if discontinued prior to 90 min). If study drug treatment is discontinued prior to 90 min, all of the scheduled 90-minute measurements will be made and recorded at the time of study drug discontinuation. Ambient CO levels will be monitored continuously using a Dräger Pac 7000 CO detector, and recorded at the time points specified below.

Table 5. CO Monitoring During Treatment

| | ABG or VBG (pH, PCO_2 , PO_2) | FiO_2 | COHb level (IL GEM Premier co-oximeter) | CO Dose Adjustment (CFK calculator) | $SpCO$ (Masimo Rad-7) | SpO_2 (Masimo Rad-7) | Ambient CO Level (Dräger Pac CO detector) |

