8.7.4.2 RELATIONSHIP TO STUDY INTERVENTION

All adverse events (AEs) will have their relationship to study intervention assessed by a designated blinded study physician at each site. Additional AE adjudication will be provided by one of the Medical Monitors who will review all AEs in an unblinded fashion as is currently recommended by the FDA for SAEs (Guidance for Industry and Investigators Safety: Reporting Requirements for INDs and BA/BE Studies (Section VI.C); December 2012). The Medical Monitors at the CCC will work collaboratively with the reporting investigator to determine if a serious adverse event has a reasonable possibility of having been caused by the study drug or procedure.

The degree of certainty about causality will be graded using the categories below. In a clinical trial, the study product must always be suspect.

- **Definitely Related** – There is clear evidence to suggest a causal relationship, and other possible contributing factors can be ruled out.
- **Probably Related** – There is evidence to suggest a causal relationship, and the influence of other factors is unlikely.
- **Possibly Related** – There is some evidence to suggest a causal relationship (e.g., the event occurred within a reasonable time after administration of the trial medication). However, other factors may have contributed to the event (e.g., the participant's clinical condition, other concomitant events).
- **Probably not related** – A clinical event, including an abnormal laboratory test result, whose temporal relationship to study intervention administration makes a causal relationship

improbable (e.g., the event did not occur within a reasonable time after administration of the study intervention) and in which other drugs or chemicals or underlying disease provides plausible explanations (e.g., the participant's clinical condition, other concomitant treatments).

- **Not Related** – The AE is completely independent of study intervention administration, and/or evidence exists that the event is definitely related to another etiology. There must be an alternative, definitive etiology documented by the clinician.

Administration related adverse events, as outlined in **Section 8.7.3** of the protocol will always be considered suspected adverse reactions if they occur within protocol-defined timeframes (**Section 8.7.3**) of study drug exposure.

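### No lactate is scheduled in the 6 hours after any dose, although a lactate rise within 6 hours is one of six events in the primary safety endpoint

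*Combined protocol and SAP*

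**What the plan says.** **The event.** The Synopsis lists "increase in lactate by ≥ 2 mmol/L" as the sixth administration-related event in the primary safety endpoint. Sections 3, 9.1 and 9.4.5 repeat the list. Sections 6.1.8, 8.7.3 and 8.7.5 add the window: "Increase in lactate by ≥ 2 mmol/L within 6 hours of study drug administration". Section 8.7.4.2 makes the window binding, since these events "will always be considered suspected adverse reactions if they occur within protocol-defined timeframes". No section says whether the 6 hours run from the start or the end of dosing.

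**The measurement.** Section 6.1.6 is a hold check: "Subjects will have blood drawn daily for measurement of COHb and lactate prior to administration of study drug". Section 8.5.2 likewise places lactate before dosing: "Lactate level will be measured and assessed daily by the local laboratory at each center prior to study drug administration". In the Schedule of Activities (Section 1.3) the lactate row carries only this footnote: "C - Measure during reference period (03:00-10:00), obtain at time closest to study drug administration if applicable". For sampling during and after dosing, Section 8.5 states: "Blood will be drawn at serial time point during treatment and after treatment for measurement of COHb levels and blood gas analysis". The table headed "Table 5. CO Monitoring During Treatment" in Section 8.5.3 has no lactate column.

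**The concern.** A laboratory event defined by a change within a fixed time needs a value before dosing and at least one value inside the window. The plan requires the first and does not schedule the second.

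The comparable components are treated differently. COHb is drawn at 20, 40, 60, 75, 90 and 180 minutes. FiO2 is repeated at 90 minutes. Ventilator parameters carry the Schedule of Activities footnote that calls for data before and after treatment; lactate does not carry it.

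Section 3 justifies the listed events as ones that could follow reduced oxygen delivery, so the lactate component belongs to the safety rationale. If it is seen only when the clinical team orders a lactate, its incidence in both arms is probably under-counted. The report could then show few or no lactate events without having looked for them in a planned way. Measurements not taken during the trial cannot be recovered at analysis.

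**Working it through.** **1. Every lactate requirement against the 6-hour window**

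| Place | What it requires | Timed post-dose lactate? |
|---|---|---|
| 6.1.4, 6.1.6, 8.5, 8.5.2 | Lactate before each day's dose | No |
| 1.3, lactate row and its footnote | One reference-period value on each of Days 1–3 | No |
| 8.5.1 with 8.5.2 | Lactate is a reference measurement, and review of those is a pre-treatment step | No |
| 8.5.3, Table 5 | COHb to 180 min; blood gas pre-dose and at 90 min (pH, PCO2, PO2) | No |
| 8.1, 8.5.2 | Recorded gas values: pH, PCO2, PO2, base excess or deficit | No |
| 8.1.1, volume table | 3 mL/day on Days 1–3, shared by blood gas, lactate and COHb | No time given |
| 6.1.5 | About 3 mL drawn during dosing, for COHb and blood gas | Lactate not named |
| 8.6.1 | Days 4, 5 and 7: lactate only if available and requested by the treating physician | Not required |

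**2. Could the next day's lactate serve?** The reference period opens at 03:00.
- Window from the start of dosing: 03:00 − 6 h = 21:00, so the dose must start after about 21:00.
- Window from the end of a 90-minute dose: the dose must end after 21:00, so it must start after about 19:30.

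This can help only doses 1 and 2. No lactate is required after dose 3.

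**3. Count.** Planned doses: 36 × 3 = 108 at most. Doses with a lactate scheduled in the window: 0.

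**4. The plan's own detection figure.** Section 9.2 and Table 6 give a 90% chance of at least one event in the CO arm at a true rate of 10%. The formula is 1 − (1 − r)^n.
- n = 24: 1 − 0.90^24 = 0.920, which does not match.
- n = 22: 1 − 0.90^22 = 0.902, which matches the printed 0.90.

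The stated 8% dropout gives 24 × 0.92 = 22.08 and 12 × 0.92 = 11.04. With n = 22 and n = 11, all 14 cells of Table 6 reproduce. The formula assumes that every event is observed.

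**5. Illustration only.** Let s be the share of true lactate events caught by a lactate that happens to be drawn in the window. The documents give no value for s, so the values below are assumptions.

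| s | CO, n = 22, r = 10%: 1 − (1 − 0.10s)^22 | CO, n = 24, same r | Placebo, n = 11, r = 15%: 1 − (1 − 0.15s)^11 | Upper 95% limit if 0 of 24 recorded |
|---|---|---|---|---|
| 1 | 0.90 | 0.92 | 0.83 | 14.2% |
| 0.75 | 0.82 | 0.85 | 0.73 | 19% |
| 0.50 | 0.68 | 0.71 | 0.58 | 28% |
| 0.25 | 0.43 | 0.46 | 0.34 | 57% |

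The last column is the exact two-sided limit 1 − 0.025^(1/24) = 0.142, divided by s. All columns apply one s to every event. If clinicians order lactate more often in deteriorating patients, capture varies with the patient's condition and these figures are only rough.

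**The case against.** - **Matching volumes.** Section 6.1.5 has about 3 mL drawn during dosing, and Section 8.1.1 budgets the same 3 mL a day for a line that names lactate. Together they could mean that lactate is part of the dosing-session sampling. They could equally refer to the pre-dose lactate. Neither gives a post-dose time, and Section 6.1.5 assigns its 3 mL to COHb and blood gas. What stands is that these lines need reconciling with Table 5.
- **Stated intent.** Sections 2.3.1 and 2.3.3 promise careful lactate monitoring but give no time point.
- **Existing capture and safeguards.** Coordinators review the previous 24 hours (8.5.2), and a blinded physician evaluates laboratory changes (8.7.5). A study physician is at the bedside during dosing and immediately available for 90 minutes afterwards (6.1.1). A blood gas with pH is taken at 90 minutes. So clinical lactates can enter the record, and an acid–base signal exists in both arms. None of this creates a lactate measurement.
- **Unseen documents.** The Manual of Operations, monitoring forms, appendices and DSMB charter were not available, and a post-dose lactate there cannot be excluded. A sample needed for a primary endpoint should still appear in the protocol's own schedule.
- **Reach.** One of six components is affected, and the accuracy endpoint is untouched by the gap. That stands.

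A reader might infer that lactate events cannot be observed at all, or that the whole safety endpoint fails. The documents support neither: clinical lactates have a route into the adverse event record, and the other five components do not depend on lactate. A reader might also take the falls in Table 6 detection as an estimate of the loss. They rest on assumed capture shares and do not carry over to the six-component endpoint.

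**Conclusion.** The concern holds for this one component. As written, the protocol and SAP text leaves a primary-endpoint event without a planned post-dose measurement after any of up to 108 doses. Its capture depends on clinically ordered lactates, so a low or zero count could not be read as evidence that lactate did not rise. The size of the under-count cannot be estimated from the documents.

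The conclusion rests on the schedule in the supplied text and on reading the two untimed 3 mL lines as setting no post-dose lactate. It would change if one of the unavailable documents already requires one. It should be corrected before further subjects are dosed, because the remedy is cheap and the missing values cannot be obtained later.

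**What to change.** For endpoint ascertainment:

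1. Add lactate in both arms to the existing 90- and 180-minute draws, in Table 5 and the Schedule of Activities, and align the volume lines in Sections 6.1.5 and 8.1.1.
2. Send these samples to the local laboratory, or otherwise report lactate separately from COHb. Sections 6.1.4 and 6.3 conceal COHb, and a shared printout could unblind the physician who adjudicates adverse events.
3. Derive the event as the highest scheduled or clinical lactate in the window minus the same-day pre-dose value.
4. State in Section 8.7.3 whether the window runs from the start or the end of dosing.
5. Report by arm how many doses had a post-dose lactate, and that the rest of the window relies on clinical samples. Section 6.1.7 times the 180-minute draw from the start of dosing. The unscheduled remainder is therefore 360 − 180 = 180 minutes (window from the start), or (90 + 360) − 180 = 270 minutes (window from the end of a 90-minute dose).

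**Cost.** At most 108 × 2 = 216 assays, a small extra blood volume (assumed 1–2 mL per treatment day), an eCRF field and a short amendment. More events will be recorded. At an assumed 10% rate per subject and current capture of 75% to 25%, the increase is at most 36 × 0.10 × (1 − s) = 0.9 to 2.7 among 36 subjects. This is an upper bound, because the later part of the window stays unscheduled. Under Section 8.7.7 each such event goes to the DSMB within 7 days, with a written report to the DSMB and FDA within 15 days.

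Each would also meet the discontinuation criterion in Section 6.1.8 as now worded, so some subjects could receive fewer doses and contribute fewer 90-minute COHb values. The sponsor must reconcile that criterion with the measurement schedule. No change to the rule is proposed here.
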